9.5.2 Safety Analysis Population

Safety analyses will be conducted in the APaT population, which consists of all randomized participants who received at least one dose of study vaccination. Participants will be included in the group corresponding to the study vaccination they actually received for the analysis of safety data using the APaT population. This will be the group to which they are randomized except for participants who take incorrect study vaccination; such participants will be included in the vaccination group corresponding to the study vaccination actually received. Safety parameters for cross-treated participants (ie, those who received vaccinations of both V114 and Prevenar 13™) will be summarized separately.

At least 1 temperature measurement obtained after study intervention is required for inclusion in the analysis of temperature.

9.6 Statistical Methods

Unless otherwise stated, all statistical tests will be conducted at the $\alpha=0.05$ (2-sided) level.

9.6.1 Statistical Methods for Immunogenicity Analyses

This section describes the statistical methods that address the primary and secondary immunogenicity objectives. Further details will be described in the sSAP. The analyses will be conducted for each of the 15 pneumococcal serotypes in V114 separately.

The between-group differences (V114 minus Prevenar 13™) in the response rates of anti-PnPs serotype-specific IgG at 30 days PD3, along with corresponding 95% CIs based on the method of Miettinen and Nurminen stratified by age category (2 months of age, ≥ 3 months of age), will be estimated. The Cochran-Mantel-Haenszel weight will be used to obtain stratum-adjusted proportion difference. The lower bound of the 95% CIs will be compared against the pre-specified margin of -0.1 to test the non-inferiority hypotheses. Other response rate analyses in immunogenicity endpoints will be performed using the same model as above. Note that the strata of 3 months of age and 4 to 6 months of age will be combined into a single stratum for the purpose of statistical analysis as the number of participants in the 4 to 6 months of age is anticipated to be very small.

Anti-PnPs serotype-specific IgG concentrations at 30 days PD3 for the 13 shared serotypes in V114 and Prevenar 13™ will be natural log-transformed and analyzed using a linear model with factors for vaccination group and age category. Between-group differences (V114 minus Prevenar 13™) and corresponding 95% CIs will be estimated on the log scale using the model above, and the results will be transformed back to the original scale to obtain the IgG GMC ratios (V114/Prevenar 13™). The lower bound of the 95% CIs will be compared against the pre-specified margin of 0.5 to test the non-inferiority hypotheses. The same model will be used to analyze IgG concentrations at 30 days PD3 for the 2 serotypes unique to V114, IgG concentrations at other timepoints, as well as OPA titers.

[Table 3](#) Summarizes key immunogenicity analyses.

Table 3 Analysis Strategy for Key Immunogenicity Variables

Endpoint/Variable (Description, Time Point)	Primary vs. Supportive Approach [†]	Statistical Method	Analysis Population	Missing Data Approach
Primary				
Anti-PnPs serotype-specific IgG response rates at 30 days PD3	P	Stratified Miettinen and Nurminen (estimate, 95% CI, p-value)	PP	Missing data will not be imputed
	S		FAS	
Anti-PnPs serotype-specific IgG GMCs at 30 days PD3 for the 13 shared serotypes	P	Linear model (estimate, 95% CI)	PP	Missing data will not be imputed
	S		FAS	
Secondary				
Anti-PnPs serotype-specific IgG GMCs at 30 days PD3 for the 2 unique serotypes	P	Linear model (estimate, 95% CI)	PP	Missing data will not be imputed
Anti-PnPs serotype-specific IgG response rates at 30 days PD4	P	Stratified Miettinen and Nurminen (estimate, 95% CI)	PP	Missing data will not be imputed
Anti-PnPs serotype-specific IgG GMCs at 30 days PD4	P	Linear model (estimate, 95% CI)	PP	Missing data will not be imputed
Anti-PnPs serotype-specific OPA GMTs at: 
 • 30 days PD3 • 30 days PD4 	P	Linear model (estimate, 95% CI)	PP	Missing data will not be imputed
Anti-PnPs serotype-specific OPA response rates at: 
 • 30 days PD3 • 30 days PD4 	P	Stratified Miettinen and Nurminen (estimate, 95% CI)	PP	Missing data will not be imputed
PnPs = pneumococcal polysaccharide, IgG = immunoglobulin G, PD = postdose, PP = Per-Protocol, FAS = Full Analysis Set, CI = confidence interval, OPA = opsonophagocytic activity [†] P = primary approach, S = supportive approach				

9.6.2 Statistical Methods for Safety Analyses

Safety and tolerability will be assessed by clinical review of all relevant parameters including AEs and postvaccination temperature measurements. Additional summaries on key safety parameters will also be provided following each vaccination.

The analysis of safety results will follow a tiered approach (Table 4). The tiers differ with respect to the analyses that will be performed. AEs (specific terms as well as system organ class terms) and other safety parameters are either pre-specified as “Tier 1” endpoints or will

be classified as belonging to “Tier 2” or “Tier 3” based on the number of participants with events.

Tier 1 Events

Safety parameters or AEs of special interest that are identified *a priori* constitute “Tier 1” safety endpoints that will be subject to inferential testing for statistical significance with p-values and 95% CIs to be provided for between-group differences in the proportion of participants with events. These analyses will be performed using the unstratified Miettinen and Nurminen method. These p-values and CIs should be regarded as helpful descriptive measures to be used in review, not formal methods for assessing the statistical significance of the between-group differences. For this protocol, solicited injection-site AEs (redness/erythema, swelling, hard lump/induration, and tenderness/pain) from Day 1 through Day 14 postvaccination and solicited systemic AEs (irritability, drowsiness/somnolence, hives or welts/urticaria, and appetite loss/decreased appetite) from Day 1 through Day 14 postvaccination are considered Tier 1 events.

Tier 2 Events

Tier 2 parameters will be assessed via point estimates with 95% CIs provided for differences in the proportion of participants with events (also via the unstratified Miettinen and Nurminen method).

In this study, membership in Tier 2 requires that at least 4 participants in any vaccination group exhibit the event. The threshold of at least 4 participants was chosen because the 95% CI for the between-group difference in percent incidence will always include zero when treatment groups of equal size each have less than 4 participants with events and thus would add little to the interpretation of potentially meaningful differences. Because many 95% CIs for Tier 2 events may be provided without adjustment for multiplicity, the CIs should be regarded as a helpful descriptive measure to be used in review, not a formal method for assessing the statistical significance of the between-group differences.

In addition to individual events that occur in at least 4 participants in any treatment group, the broad AE categories consisting of the proportion of participants with any AE, a vaccine-related AE, an SAE, a vaccine-related SAE, discontinuation due to an AE, and death will be considered Tier 2 endpoints. The proportion of participants with maximum temperature measurements meeting particular points (≥ 37.5 °C, ≥ 38.0 °C, ≥ 39.0 °C, ≥ 40.0 °C) will also be considered Tier 2 endpoints.

Tier 3 Events

Safety endpoints that are not Tier 1 or 2 events are considered Tier 3 events. Only point estimates by treatment group are provided for Tier 3 safety parameters.

Medical device incidents due to syringe, if any, will be listed.

Table 4 Analysis Strategy for Safety Parameters

Safety Tier	Safety Endpoint [†]	p-Value	95% CI for Between-Group Comparison	Descriptive Statistics
Tier 1	Injection-site redness/erythema (Days 1 to 14)	X	X	X
	Injection-site swelling (Days 1 to 14)			
	Injection-site tenderness/pain (Days 1 to 14)			
	Injection-site hard lump/induration (Days 1 to 14)			
	Irritability (Days 1 to 14)			
	Drowsiness/somnolence (Days 1 to 14)			
	Hives or welts/urticaria (Days 1 to 14)			
	Appetite loss/decreased appetite (Days 1 to 14)			
Tier 2	Any AE [†]		X	X
	Any Vaccine-related AE [†]			
	Any SAE [†]			
	Any Vaccine-related SAE [†]			
	Discontinuation due to AE [†]			
	Death [†]			
	Maximum temperature measurements meeting cut points (≥ 37.5 °C, ≥ 38.0 °C, ≥ 39.0 °C, ≥ 40.0 °C; Days 1 to 7)			
	Specific AEs by SOC and PT [‡] (incidence ≥ 4 participants in at least one of the vaccination groups)			
Tier 3	Specific AEs by SOC and PT [‡] (incidence < 4 participants in all of the vaccination groups)			X

AE = adverse event; CI = confidence interval; PT = preferred term; SAE = serious adverse event; SOC = system organ class; X = results will be provided.

[†] These endpoints are broad adverse event categories. For example, descriptive statistics for the safety endpoint of “Any AE” will provide the number and percentage of participants with at least one AE.

[‡] Includes only those endpoints not pre-specified as Tier 1 or not already pre-specified as Tier 2 endpoints.

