6.3.2 Stratification

Intervention randomization will be stratified according to the age category (2 months, 3 months and 4 to 6 months of age).

Each age category is defined as follows:

- 2 months of age category : 2 months of age to 1 day prior to 3 months of age
- 3 months of age category : 3 months of age to 1 day prior to 4 months of age
- 4 to 6 months of age category : 4 months of age to 1 day prior to 7 months of age

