9.10 Subgroup Analyses

The IgG response rates and IgG GMCs at 30 days PD3 will be analyzed separately by age category (2 months of age, ≥3 months of age; 2 months of age, 3 months of age, 4 to 6 months of age). The IgG response rates will be analyzed using the unstratified Miettinen and Nurminen method, and IgG GMCs will be analyzed using a linear model with a term for vaccination group. Additional subgroup analyses, if any, will be documented in the sSAP.

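### Tier 1 solicited-AE comparisons leave out the age stratification used in randomisation and in the immunogenicity comparisons, and no reason is given (optional improvement)

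*Protocol*

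**What the plan says.** - **Randomisation.** Protocol 6.3.2: "Intervention randomization will be stratified according to the age category (2 months, 3 months and 4 to 6 months of age".
- **Immunogenicity response rates.** Protocol 9.6.1 uses the Miettinen-Nurminen method stratified by age at two levels (2 months; 3 months and over). On weights: "The Cochran-Mantel-Haenszel weight will be used to obtain stratum-adjusted proportion difference". On the other endpoints: "Other response rate analyses in immunogenicity endpoints will be performed using the same model as above". It merges the two older groups because few infants aged 4 to 6 months are expected: "the strata of 3 months of age and 4 to 6 months of age will be combined into a single stratum".
- **Concentrations and titers.** The same section uses a linear model with factors for vaccination group and age category. sSAP 3.6.1 repeats all of this.
- **Age subgroups.** Protocol 9.10 and sSAP 3.10 drop the stratification: "The IgG response rates will be analyzed using the unstratified Miettinen and Nurminen method". This is natural, because age defines the subgroup.
- **Tier 1 safety.** Eight solicited events get a p-value and a 95% CI. Protocol 9.6.2: "These analyses will be performed using the unstratified Miettinen and Nurminen method". Protocol 9.1, sSAP 3.1 and sSAP 3.6.2 say the same. On their status: "These p-values and CIs should be regarded as helpful descriptive measures to be used in review".
- **Tier 2 safety.** Intervals only, "also via the unstratified Miettinen and Nurminen method".

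**The concern.** When randomisation is stratified on a factor, the usual default is to carry that factor into the analysis. An analysis that ignores it estimates the standard error as if between-stratum variation were chance variation between the arms, although the design has removed most of it. The plan follows the default for immunogenicity and departs from it for Tier 1 without comment. The only remark about strata explains why two of them are merged, not why age is dropped for safety.

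The descriptive label on Tier 1 does not account for the difference. The secondary response rates carry no hypothesis either, and they are stratified.

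The stake is small. Solicited events are the endpoints of primary Objective 1, and an interval that is slightly too wide makes a real reactogenicity difference slightly harder to see.

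**Working it through.** **1. The plan's own figure.** Protocol Table 6 assumes 330 per arm, two-sided 5% and about 80% power. With a null difference of zero, the Farrington-Manning calculation reduces to the pooled score test:

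power = Φ{[p1 − p2 − 1.96·√(2p̄(1−p̄)/n)] / √([p1(1−p1) + p2(1−p2)]/n)}

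For 40.4% against 30.0% this gives 80.0%. All seven rows give 79.6% to 80.6%. The table is correct for the unstratified method.

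**2. Inputs that must be assumed.** The documents do not give the share of infants in each age group or event rates by age. Assumed shares (2 / 3 / 4 to 6 months) are 80/15/5% and 70/20/10%. Four sets of assumed event rates are in the table below. The two older groups are merged, as in 9.6.1.

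**3. Effect on interval width.** With equal allocation within strata, the ratio of stratified to unstratified variance is

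R = Σ w_g·p_g(1−p_g) / [p(1−p)], and the interval narrows by 1 − √R.

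Worked example, shares 70/20/10% and rates 60/40/30%:
- merged older stratum: (0.2×0.4 + 0.1×0.3)/0.3 = 0.3667
- overall rate: 0.7×0.6 + 0.3×0.3667 = 0.53, so p(1−p) = 0.2491
- numerator: 0.7×0.24 + 0.3×0.3667×0.6333 = 0.2377
- R = 0.2377/0.2491 = 0.9541, so √R = 0.9768 and the interval is 2.32% narrower
- half-width: 1.96·√(2×0.2491/330) = 7.62 points; ×0.9768 = 7.44 points

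| Rates by age (%) | R, shares 80/15/5 | Narrower by | R, shares 70/20/10 | Narrower by |
|---|---|---|---|---|
| 50/40/35 | 0.9919 | 0.41% | 0.9885 | 0.58% |
| 60/40/30 | 0.9672 | 1.65% | 0.9541 | 2.32% |
| 20/25/30 | 0.9963 | 0.19% | 0.9946 | 0.27% |
| 20/30/40 | 0.9857 | 0.72% | 0.9795 | 1.03% |

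**4. Type I error and power.** These come from simulation with 200,000 trials per scenario, 330 per arm and true differences of 9.6 to 10.9 points.
- Type I error: 0.042 to 0.050 unstratified, 0.048 to 0.051 stratified.
- Power gain: 0.1 to 0.9 points. The largest is 79.5% to 80.4%, in the worked example.
- In the worked example the variance formula alone gives an unstratified type I error of 2[1 − Φ(1.96/0.9768)] = 0.045. The rest of the drop to 0.042 comes from the count difference being a whole number.
- With rates flat across age at 5% to 50%, power differs by at most 0.1 point.

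**5. Rare events.** Take 4 events against 0, with 330 per arm and strata of 248 and 82 per arm (assumed). The unstratified lower limit is 0.053 points. The stratified lower limit is 0.028 to 0.058 points, depending on which stratum holds the events. Zero is excluded either way, so a rule that switches method on observed counts is not needed.

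**The case against.** The strongest reply is that nothing is broken. The method is stated consistently in four places, an unstratified score interval after stratified randomisation is valid, and Table 6 matches it. Tier 1 results are declared descriptive and no decision rule depends on them. Safety now has one uniform method, and the secondary response rates may simply follow the primary immunogenicity model. All of this stands, and it is why the point is optional.

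It is also fair that age at first dose may matter little. Tier 1 counts events after any of four doses, and every infant is due Dose 4 at 12 to 15 months of age. The gain could then be close to nil.

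Two objections to the remedy have weight. First, stratifying Tier 1 alone would treat irritability differently from the category of any AE that contains it, so the plan should say why Tier 2 differs. Second, protocol section 9 lets non-confirmatory changes go into the sSAP, but sSAP section 1 limits itself to changes that are not principal and that arise from information unavailable when the protocol was finalised. The age strata were already known, so both documents should change together.

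A reader might infer more than the documents support:
- **That the Tier 1 estimates are biased.** They are not. With equal arm counts within strata the two point estimates coincide, and otherwise they nearly do.
- **That the safety power is wrong.** It reproduces.
- **That the gain is substantial.** Over a wider assumed grid, an age gap of 20 points in event rates raises power by up to 2.4 points (81.2% to 83.6% at 10.9% against 5%). Nothing in either document supports a gap of that size.

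**Conclusion.** The point holds as a low-severity, optional improvement. Tier 1 omits a factor that the trial randomises on and uses in its other between-group comparisons, and the plan does not say why. The current analysis is valid and at most slightly conservative, and no stated power, alpha or sample size needs correcting.

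Under the eight base scenarios, stratifying would narrow the intervals by about 0.2% to 2.3%, add up to about 1 point of power and bring type I error to about 0.05. These figures depend wholly on assumed age shares and assumed age-specific event rates. If rates are flat by age, there is neither material gain nor material loss.

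**What to change.** In protocol 9.6.2 and sSAP 3.6.2, and in the summaries at protocol 9.1 and sSAP 3.1:
- Analyse all eight Tier 1 endpoints with the stratified Miettinen-Nurminen method and Cochran-Mantel-Haenszel weights of 9.6.1. Use the two age strata (2 months; 3 months and over), with no switch based on observed counts.
- Keep the unstratified Tier 1 result as a sensitivity analysis.
- State that Tier 2 stays unstratified, because it includes event terms that are selected by the data and are often sparse.
- Leave the immunogenicity methods, the age-subgroup analyses and Table 6 as they are.

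Make the change before unblinding, and align the protocol and sSAP wording at the same time. The cost is wording in four places and a method already specified for immunogenicity. No new data or extra participants are needed, because the age category is known for every randomised infant, including those grouped by vaccine received. If the sponsor prefers the present method, one sentence giving the reason would close the point.

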9.6.3 Summary of Baseline Characteristics

The comparability of the vaccination groups for each relevant demographic and baseline characteristic will be assessed using summary tables. No statistical hypothesis tests will be performed on these characteristics. The number and percentage of participants screened and randomized and the primary reasons for screening failure and discontinuation will be displayed. Demographic variables (eg, age, gender, birth weight, and gestational age), baseline characteristics, prior and concomitant vaccinations and therapies will be summarized by vaccination group either by descriptive statistics or categorical tables.

9.7 Interim Analyses

No interim analysis is planned for the study.

9.8 Multiplicity

The study will be considered to have met its primary immunogenicity objective if non-inferiority is demonstrated in the IgG response rates for the 15 serotypes and in the IgG GMCs for the 13 shared serotypes, both at 30 days PD3. Successful achievement of the primary immunogenicity objective requires that all individual serotypes within the hypotheses satisfy the pre-specified non-inferiority criteria at a 1-sided α level of 0.025. This approach will control the 1-sided type I error rate at 0.025, thus no multiplicity adjustment will be required.

No multiplicity adjustments will be made for the safety objective.

9.9 Sample Size and Power Calculations

9.9.1 Sample Size and Power for Immunogenicity Analyses

A total of 660 participants will be randomized in a 1:1 ratio to V114 or Prevenar 13™ to have 300 participants per arm in the PP population at 30 days PD3 (~90% evaluability rate). The study will have an overall power of ~83% for all the primary hypotheses at a 1-sided α level of 0.025. The power calculations for the individual hypotheses are provided below.

Primary endpoints/hypotheses (H1 and H2)

The study will have a power of ~83% at a 1-sided α level of 0.025 to demonstrate that V114 is non-inferior to Prevenar 13™ for the 13 shared serotypes and the 2 unique serotypes in the anti-PnP serotype-specific IgG responses rates at 30 days PD3. The underlying serotype-specific response rates are based on the results from V114 Protocol 008 (safety and immunogenicity of two different lots of V114 were evaluated; Lot 1 and Lot 2 pooled for V114), as listed in [Table 5](#) below.

Table 5 Assumptions of the True Response Rates at 30 Days PD3

Serotype	True Response Rate	
	V114	Prevenar 13™
Prevenar 13™ Types		
1	0.972	0.969
3	0.951	0.718
4	0.976	0.951
5	0.960	0.966
6A	0.931	0.962
6B	0.914	0.914
7F	0.995	0.990
9V	0.975	0.958
14	0.984	0.972
18C	0.975	0.955
19A	0.987	0.986
19F	0.995	0.997
23F	0.936	0.907
Non-Prevenar 13™ Types		
22F	0.987	0.907 [†]
33F	0.889	0.907 [†]

[†] Serotype 23F; Based on Phase 2 data, serotype 3 had the lowest response rate for PCV13, however, for the purpose of power calculation, the serotype with the next lowest response rate, 23F, was used.

Primary endpoints/hypotheses (H3)

This study will have a power of >99% at a 1-sided α level of 0.025 to demonstrate V114 is noninferior to Prevenar 13™ for the 13 shared serotypes based on the anti-PnP serotype-specific IgG GMCs at 30 days PD3. The power calculations are based on the true IgG GMC ratio of 1.0 and the true standard deviation of natural log IgG concentration of 1.1 for all shared serotypes.

9.9.2 Sample Size and Power for Safety Analyses

The probability of observing at least 1 SAE in this study depends on the number of participants vaccinated and the underlying incidence of participants with an SAE in the study population. Calculations below assume that 100% of the randomized participants will be evaluable for safety analyses. There is an 80% chance of observing at least one SAE among 330 participants in each of the V114 group and Prevenar 13™ group if the underlying incidence of an SAE is approximately 0.49% (1 of every 206 participants receiving the vaccine). There is a 50% chance of observing at least one SAE among 330 participants in each of the V114 group and Prevenar 13™ group if the underlying incidence of an SAE is approximately 0.21% (1 of every 477 participants receiving the vaccine). If no SAEs are observed among 330 participants in each of the V114 group and Prevenar 13™ group, this study will provide 97.5% confidence that the underlying percentage of participants with an SAE is approximately <1.1% (one in every 90 participants).

Table 6 summarizes the percentage point differences between the 2 vaccination groups that could be detected with ~80% probability for a variety of hypothetical underlying incidences of an adverse event. These calculations assume 330 participants in each group and are based on a 2-sided 5% alpha level. The calculations are based on an asymptotic method proposed by Farrington and Manning [Farrington, C. P. 1990]; no multiplicity adjustments were made.

Table 6 Differences in Incidence of Adverse Events Between the 2 Vaccination Groups That Can be Detected With an ~80% Probability (Assuming 2-sided 5% Alpha Level With 330 Participants in Each Group)

Incidence of Adverse Event		Risk Difference
V114 (%) N=330	Prevenar 13™ (%) N=330	Percentage Points
2.6	0.1	2.5
6.4	2.0	4.4
10.9	5.0	5.9
17.5	10.0	7.5
23.6	15.0	8.6
29.4	20.0	9.4
40.4	30.0	10.4

Incidences presented here are hypothetical and do not represent actual adverse experiences in either group. Based on an asymptotic method proposed by Farrington and Manning [Farrington, C. P. 1990]

